Step 3. Review with YAB. Drs. [name] and [name] will facilitate the review of the mLab App user interface, content, and function with the YAB. Through our review, we will ensure that the mLab App is culturally appropriate for both YMSM and YTGW. [name] will insert changes directly into the mLab App mock-ups viewed on a screen, supplemented by note-taking by study staff and audio-recorded. This allows us to confirm meaning, make revisions as necessary, and reach consensus with the YAB. [name] will probe for further discussion on feasible ways forward and to ensure that the mLab App meets the current prevention guidelines. We will incorporate the recommended changes. As a final step, we will have members of the YAB test the final mLab App after the meeting in their own settings (e.g., Home) and return any comments or additional edits within 2 weeks. Final recommendations for the user interface will be shared with [name], who will work with his team and the graphic design team at Little Green Software (see letter of support) to make the final updates to the app.

Aim 2: Evaluate the efficacy of the mLab App in improving both HIV testing rates and linkage to care versus standard preventive care in 525 Black, Latino and other young men and transgender women (inclusive of YMSM and YTGW age 18-29 years) in a 12-month multi-site trial, with randomization at each site to three groups arm 1: intervention (mLab App) (N=210); arm 2: standard of care HIV information control arm (N=210); arm 3: OraQuick home test kits only (N=105).

Hypothesis 1. Youth randomized to the mLab App arm, as compared to youth in the standard of care HIV information control arm, will have: a) increased rates of HIV testing within the first 6 months of the trial; and b) increased rates of re-testing in months 7-12 of the trial.

Hypothesis 2. The total number of youth who test HIV positive and link to care in the mLab App arm will be greater as compared to the standard of care HIV information control arm.

Hypothesis 3. The image processing in the mLab App will: 1) have no statistically significant difference in sensitivity or specificity when compared to confirmatory testing, 2) have greater sensitivity and specificity when compared to the user-submitted self-analyses.

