mLab Image-Processing Evaluation Methods. During use of the mLab App, participants will submit images of their Oraquick self-test to the app for analysis by an automated image-processing algorithm. Prior to submitting this image for analysis, participants will be asked to interpret the results of the test using the instructions that are provided standard with the OraQuick test. This self-reported result will be recorded and uploaded with the user-submitted image of their rapid test. Study team members with expertise in rapid test use and analysis will evaluate the uploaded images of each rapid test, and provide an additional assessment. The user-submitted result and the study team assessment will not be used by mLab in its automated image-processing. All users that submit tests that are identified as positive, either by the automated image-processing in mLab, the study team personnel's inspection of the image of the rapid test, or by the study participant themselves, will be referred for confirmatory testing.

(*Hypothesis 3*).**mLab Image-Processing Data Analysis Plan.** Including the confirmatory test, which will be treated as the gold standard to determine whether a test result is truly false or positive, there will be results from four analysis methods collected on the same set of tests (1. User-submitted results, 2. Study team interpretation of uploaded images, 3. Automated mLab App results, 4. Confirmatory testing). The sensitivity and specificity for each of these methods will be compared using McNemar's test. This will result in the following statistical comparisons for both sensitivity and specificity: 1) user-submitted analysis to study team analysis, 2) user-submitted analysis to mLab analysis, 3) study team analysis of uploaded images, 4) user-submitted analysis to confirmatory testing, 5) study team analysis to confirmatory testing, 6) mLab analysis to confirmatory testing.

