Missing Data. Multiple imputation (MI) methods will be applied to address missing values under the missing at random (MAR) assumption (i.e., missingness can be fully accounted for by variables with complete information).¹⁴¹ These analyses will be complemented with assessment of how sensitive the inferences are to the MAR assumptions. Sensitivity analysis will be performed based on selection models for dropout.¹⁴²⁻¹⁴⁴ Intention-to-Treat (ITT) Analysis: All analyses will use the ITT principle,¹⁴⁵ which requires subjects' data to be analyzed as randomized, regardless of whether they used the mLab App or not.

Aim 3: Monitor and analyze paradata to understand the effect of user engagement of the mLab App on improving HIV testing rates and linkage to care.

To understand barriers and/or facilitators of its use, the mLab app will automatically collect paradata for each user interaction throughout the study. This paradata is considered "free" in that it does not require any additional effort from the user.¹⁴⁶ This data will be analyzed for each user, as well as aggregated to understand what component of the intervention lead to behavior change. We will specifically examine who uses the mLab App and how frequently it is used over time.

Methods. We will capitalize on the use of the extant mLab software which is written as a mobile-friendly web application in hypertext markup language (HTML), hypertext preprocessor (PHP), JavaScript, and Python (for computer vision), and integrates with REDCap for backend data storage. On each page of the mLab app, a PHP script logs every user interaction before the page of the application is displayed to the user. Therefore, any event that would refresh or send the user to a new page (e.g., HTML links) initiates an event-driven paradata capture. The PHP script transmits the data to REDCap through the secure REDCap API.

Data Analysis. The primary paradata that will be collected is shown in Table 4. From this data, we will derive the following use data for each session: duration on each page, page progression through the application, time from login to result, number of rapid test pictures previewed before sent for result, and total time prior to logout. We will analyze the data on multiple scales and perspectives: individual-level (i.e. user-level), application-level, page-level, session-level, and how these differ by demographic characteristics, HIV testing history, technology

Table. Paradata Collected for Each mLab Event

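### Hypothesis 3, part 1 is met by a non-significant McNemar test of the app against its own gold standard, so the verdict turns on the number of errors, and no reference result is planned for tests that every reader calls negative

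*Combined protocol and SAP*

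**What the plan says.** Hypothesis 3, part 1 (Study Aims, repeated under Aim 2) is that the image processing will "have no statistically significant difference in sensitivity or specificity when compared to confirmatory testing". The mLab Image-Processing Data Analysis Plan makes that same confirmatory test the arbiter: "Including the confirmatory test, which will be treated as the gold standard to determine whether a test result is truly false or positive". It continues: "The sensitivity and specificity for each of these methods will be compared using" McNemar's test, in six comparisons. The last three set the user, the study team and the app against confirmatory testing. The version of the test is not stated. The Data Analysis section sets two-sided 0.05. No margin, performance goal or sample size is given for Hypothesis 3; the sample size section covers Hypothesis 1 only.

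The plan expects that "there will be results from four analysis methods collected on the same set of tests". The Evaluation Methods paragraph, however, refers for confirmation only on a positive read by the app, the team or the participant: "All users that submit tests that are identified as positive, either by the automated image-processing in mLab" and so on. What happens after a negative result differs by section:

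- The procedures for a reactive test (intervention arm) refer after a negative only on request, and the OraQuick risk section is similar.
- The Arm 1 description and the consent section advise confirmation after negatives too.
- The intervention-arm risk list makes further testing available to everyone.
- The benefits section refers sero-negative app users to standard services, including testing, at the end of the study.

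None of these says that the results are captured for the analysis.

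**The concern.** There are two separate problems.

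**Decision rule.** Failing to find a difference is treated as evidence of none. Because the comparator defines the truth, its sensitivity and specificity are 100% by construction. The test can therefore only ask whether the app's error count is clearly above zero. Few tests make success easier, and many make it harder, at the same accuracy.

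**Verification.** Whether a test gets a reference result depends on how it was read. Specificity computed on verified tests leans heavily on false positives. Infected strips that every reader calls negative drop out of sensitivity. The protocol itself accepts that the test can miss infection.

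At stake is the trial's accuracy statement for a reader that the protocol calls investigational.

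**Working it through.** The plan gives no figure of its own for Hypothesis 3, so there is nothing to reproduce. Figures in brackets use the uncorrected test.

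**1. The cut-off.** Let b be the number of app errors. The opposite discordant cell is always 0. Exact p = 2 × 0.5^b, uncorrected χ² = b, corrected χ² = (b − 1)²/b.

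| Version | Last non-significant | First significant |
|---|---|---|
| Exact | b = 5, p = 0.0625 | b = 6, p = 0.031 |
| Continuity-corrected | b = 5, p = 0.074 | b = 6, p = 0.041 |
| Uncorrected | b = 3, p = 0.083 | b = 4, p = 0.046 |

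The number of tests appears in none of these formulas.

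**2. Chance of passing.** P(pass) = P(Binomial(n, error rate) ≤ 5), or ≤ 3.

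Inputs from the documents: 210 participants in arm 1, up to four kits each (210 × 4 = 840), and 25–40 expected positives. Assumptions: positives spread 2:2:1 over the arms, so 40% or 10–16 fall in arm 1; 824 = 840 − 16 is the most uninfected tests possible with 16 infected; 200 stands for low uptake; accuracies are illustrative; tests are independent, although one person can contribute four.

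| Leg | Assumed accuracy | n | P(pass) |
|---|---|---|---|
| Sensitivity | 70% | 10 infected | 95% (65%) |
| Sensitivity | 70% | 16 infected | 66% (25%) |
| Specificity | 99% | 200 uninfected | 98% (86%) |
| Specificity | 99% | 824 uninfected | 17% (4%) |

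Part 1 names both measures. For a 70%-sensitive, 99%-specific app with 10 infected among 400 tests (390 uninfected), both legs pass with probability 0.953 × 0.801 = 0.76 (0.650 × 0.452 = 0.29).

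**3. Specificity on verified tests.** Assume app, user and team specificities of 98%, 98.5% and 99.5%, independent errors, and every flagged test confirmed. The share of uninfected tests read negative by all three is 0.98 × 0.985 × 0.995 = 0.9605. Of 390 uninfected tests, 15.4 are flagged, 374.6 are all-negative, and 390 × 0.02 = 7.8 are app false positives.

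| All-negatives verified | Verified uninfected tests | Apparent app specificity (true 98%) |
|---|---|---|
| 0% | 15.4 | 1 − 7.8/15.4 = 49% |
| 10% | 15.4 + 37.5 = 52.9 | 85% |
| 25% | 15.4 + 93.6 = 109.1 | 93% |

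**4. Sensitivity on verified tests.** Suppose 5% or 10% of infected strips show no line, and app, user and team read 80%, 90% and 98% of visible lines. True app sensitivity is 0.8 × 0.95 = 76% or 0.8 × 0.90 = 72%. If only flagged tests are verified, it shows as 0.8/(1 − 0.2 × 0.1 × 0.02) = 80% in both cases.

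**5. Does the Missing Data section cover this?** It says: "Multiple imputation (MI) methods will be applied to address missing values under the missing at random (MAR) assumption", with sensitivity analysis by selection models for dropout. Neither is aimed at unverified tests. All-negative tests with a reference result would come mainly from participants who chose to seek testing.

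**The case against.** Several objections have force.

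- **All-negatives are not simply abandoned.** Four places advise, offer or refer for testing after a negative, so a reader cannot infer that most such tests will lack a reference result. That is right: the verified share is unknown. What stands is that no step obtains or records those results for this analysis.
- **The 49% is not a forecast.** It assumes that no all-negative test is verified and that every flagged user completes confirmation. The plan only refers them. The 85% and 93% show how quickly the figure moves.
- **A reader might infer that missing negatives also corrupt the specificity p-value.** They do not if all flagged tests are confirmed, because missing uninfected all-negatives are concordant pairs. The estimate is distorted, not that test.
- **A reader might infer that part 2 (app versus user) is either invalid or wholly untouched.** Neither holds. The flaw in the decision rule does not reach it, and its discordant pairs all contain a positive read and so are referred. But it loses pairs if flagged users do not complete confirmation.
- **No formal consequence is attached to passing.** True; success is read from the wording of the hypothesis. Accuracy is a secondary goal, the protocol says that it is unproven, and the manual read is the result of record. This limits the severity but does not make the criterion informative.

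**Conclusion.** The concern holds for part 1 of Hypothesis 3. The dependence on error count alone is exact arithmetic for the standard McNemar versions; only the cut-off (5 or 3) varies. The pass rates rest on assumed test counts and accuracies. They show the direction: a poor reader can pass on few tests and a good one fail on many. They do not show that accuracy is irrelevant.

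The verification gap also holds, in limited form: no reference result is planned for all-negative tests, the share verified is unknown, and the sections on testing after a negative must be reconciled. A complete-case analysis would understate specificity, and would overstate sensitivity if every reader misses some infected strips. The size of either bias cannot be fixed from the documents.

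The primary comparison is unaffected. This should be fixed, but it does not threaten the trial's main result.

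**What to change.** 1. Drop the no-significant-difference criterion and the McNemar comparisons against confirmatory testing (4 to 6). Report sensitivity and specificity with 95% confidence intervals that allow for repeat tests per participant, for example by a participant-level bootstrap, with exact limits where there are no errors.
2. For strip reading by the app and the user, take the study-team read as reference. It is already planned: the team "will evaluate the uploaded images of each rapid test". Record it before the app and user results are opened, then open them so that the planned contact over discrepancies can go ahead.
3. Run no McNemar test of a method against its own reference. Test part 2 (app versus user) by McNemar with the team read as reference on all images, and repeat it with confirmatory results on the verified subset.
4. Complete the third listed comparison, which names only one method: "3) study team analysis of uploaded images, 4) user-submitted analysis to confirmatory testing". The missing pair is team versus app. Report comparisons 1 and 3 as agreement, or as estimates against the team read.
5. Report confirmatory results as positive predictive value among flagged tests, with the number who completed confirmation. Limit any statement about HIV status to the verified tests, described as a selected set, and say that unverified tests are not imputed.
6. Reconcile the sections on testing after a negative result, and state whether those results are recorded.

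The cost is plan wording and the timing of an existing read; no new readers, tests or visits. The downsides should be stated. Part 1 becomes an estimate rather than a yes/no hypothesis. The claim narrows to reading the strip correctly. Image faults that mislead both team and app go undetected. The sensitivity interval is wide: with no misses the exact lower limit is 0.025^(1/n), or 0.69 for 10/10 and 0.79 for 16/16.

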Scientific Premise. YMSM and YTGW currently face barriers to HIV testing in clinics (e.g., socioeconomic

Overview of Study Aims, Design and Methods. Table 1 presents an overview of the design, participants, and data analysis plan for each aim.

Scientific Rigor. We will use a careful iterative process to refine the usability and test the efficacy of the mLab App for increasing the uptake of rapid home HIV self-testing. To increase scientific rigor we will: 1) have an image of the participants’ OraQuick test result ensuring the validity of self-reported testing collected via

surveys; 2) use validated measures; 3) use a randomized design to reduce bias in study arm assignment; 4) exercise extensive retention efforts to achieve high retention and reduce selection bias; 5) publish our design and analysis plan on clinicaltrials.gov before we commence data collection; 6) publish anonymized public use data sets after primary analyses are reported. Consideration of sex as a biological variable. We do not aim to

Table 1. Overview of Design, Methods, Participants, and Data Analysis

Aim	Design/Methods	Participants	Data Analysis
1	Usability Evaluation	Heuristic evaluation: human-computer interaction experts (N=5); End-User testing: YMSM and YTGW (N=20); Youth Advisory Board (N=10)	Quantitative and qualitative summary of heuristic violations; thematic analysis of think-aloud protocol, quantitative summary of mouse clicks, time, etc.
2	Randomized controlled design	High-risk YMSM and YTGW (N=525; arm 1 n=210, arm 2 n=210, arm 3 n=105)	Descriptive statistics; Linear regression model
3	Analysis of Para Data	Data Collected through Participant use of the mLab App (N=210)	

evaluate sex differences; the justification for only including assignment of male sex at birth is that the epidemiologic data demonstrate a clear, disproportionate impact of HIV on young racial and ethnic minority men.

Aim 1: Refine the mLab App – a mobile and connected health intervention for increasing the uptake of rapid home HIV self-testing and linkage to care – by employing rapid cycle iterative design methods with feedback from human computer interaction experts (N=5), end-users (N=20), and youth advisory board members (N=10). There are three steps with refinements to the mLab App following each step. Step 1.

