Arm 1-Intervention Arm (mLab App + HIV home test). Youth randomized to the intervention arm will be provided with the mLab App, 2 OraQuick tests (including the package insert), and a box of condoms to take home at baseline. They will receive 2 more OraQuick tests at their 6 month visit. Participants may come in person to receive their tests or their tests may be mailed to them at their verified address if they are unable to complete the in-person visit. The OraQuick tests will be sent via tracked shipping through USPS, FedEx, and UPS. At their baseline appointment, youth will also be sent an email or text with links to mobile-optimized online prevention information, including PrEP and HIV testing information that is found on the CDC website. They will also receive a study information card listing the Columbia University School of Nursing / Lurie Children's study teams' contact information. The goal of the mLab App is not for partner testing. We will advise participants upon study enrollment and consent (see Protection of Human Subjects) that the technology is NOT to be used for this purpose in this study. Given this limitation, we will suggest that participants who have partners who are interested in testing should contact the study team in each respective city for more information on HIV testing. We will also reinforce with participants that the mLab App is considered a screening device and they should seek confirmatory testing (for both negative and positive test results). The mLab App is mobile app on your phone that is accessible using a login name and password. The app will provide HIV prevention information, push notification reminders for testing, step-by-step instructions for using the OraQuick HIV tests, an image upload function to send an image of your OraQuick HIV test to the study team.

Participants will:

- a) be asked to manually enter the Oraquick test results; and
- b) take a picture of the test results for the app to analyze the results; and

- c) receive the app's interpretation of the Oraquick test results.

By using the app, we are asking participants to help test the app's ability to interpret the results of the OraQuick tests. If you test HIV positive by the OraQuick HIV test and/or the mLab app will provide information on how to set up follow-up confirmatory testing within the following 24 hours. All information that you provide within the app will be stored on a secured server at Vanderbilt University

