Reminder notifications. Participants in the intervention arm will be instructed to use the mLab App and the HIV self-test kit at 3 months, 6 months, 9 months, and 12 months after enrollment. Participants will receive a reminder push notification 2 weeks prior to their scheduled test date and 1 week after their scheduled test date.¹³⁸ In the mLab app, if a participant indicates they have received a preliminary positive HIV test using the home HIV test, participants will be directed to another screen on their smartphone directing them to call the study team or the warm line at the NYP or Lurie clinic (depending on geographic location) to receive follow-up confirmatory testing [and if needed, linkage to care]. Participants will be told that this result does not necessarily indicate that they are HIV positive (see false positive in Protection of Human Subjects), that further follow-up testing is needed, and they should contact the clinic or the study team within 24 hours. The mLab team will return the call within normal business hours. The number and nature of calls from participants to the study team (e.g., related to mLab App use, test interpretation, distress at reactive results) will all be recorded and will be reviewed yearly or at a date determined by the DSMB with our DSMB (see letters of support). We will track linkage to follow-up testing and care. Our DSMB will carefully monitor our study activities and data – see Data Safety and Monitoring Plan. **Sound Retention Efforts.** Participants will be asked after study screening what would be the best way for us to remind them of the appointment (voice phone, text, e-mail). Participant retention during the intervention will be enhanced in several ways. First, participants will be compensated for their time to complete the baseline assessment and completing the follow-up assessments. In addition, during the follow-up survey (6 months), participants will be asked to update their locator information. Using these extensive procedures promotes participant attendance at the follow-up visits, which has been shown to be successful in previous trials.^{139, 140} **We have 4 levels of outcomes:** primary, secondary, intermediate, and program evaluation. The survey items are included in the Qualtrics attachment. The primary outcome for Aim 2 / study trial (Uptake of rapid HIV

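### Hypothesis 3 uses McNemar's test on individual rapid tests with no allowance for up to four tests per participant; if disagreements repeat within a person, the p-values are too small, mainly for specificity

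*Combined protocol and SAP*

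**What the plan says.** The combined protocol and SAP sets out the Hypothesis 3 analysis under Aim 2, in the mLab Image-Processing Evaluation Methods and Data Analysis Plan. Study team members "will evaluate the uploaded images of each rapid test, and provide an additional assessment", so every uploaded test is read. The plan then says that "there will be results from four analysis methods collected on the same set of tests", the four being the user's reading, the study team's reading, the app's result and the confirmatory test. The method is given in one sentence: "The sensitivity and specificity for each of these methods will be compared using McNemar's test". It does not say whether the exact or the asymptotic version is meant.

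The number of tests per person comes from two other places. The Arm 1 description hands out two kits at baseline and adds: "They will receive 2 more OraQuick tests at their 6 month visit". Under Reminder notifications, arm 1 participants are "instructed to use the mLab App and the HIV self-test kit at 3 months, 6 months, 9 months, and 12 months after enrollment". Table 1 gives the arm sizes: "arm 1 n=210, arm 2 n=210, arm 3 n=105".

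The Hypothesis 3 text, the Data Analysis section and the Missing Data section contain no cluster adjustment, participant-level summary or one-test-per-person rule. Aim 3 does plan a longitudinal analysis of repeated use, but for user experience, not for reading accuracy.

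**The concern.** McNemar's test compares two readings on matched pairs and treats the pairs as independent. Here up to four pairs come from one person, usually with the same phone and the same reading habits. The protocol itself names sources of error that could recur: lighting and geometry of the image (risks specific to the app), differences between devices and browsers (Aim 3), and difficulty reading weak bands (Background). Someone whose first test produces a disagreement between self-reading and app may well produce another.

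If so, the discordant pairs carry less information than their number suggests, and the p-value is too small. The two parts of Hypothesis 3 are affected in opposite directions. Part 2, that the app is more accurate than self-reading, would be declared too often. Part 1 predicts no statistically significant difference from confirmatory testing, so p-values that are too small work against it. App reading performance is the trial's stated secondary goal.

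**Working it through.** **The plan's own figure.** The Data Analysis section sets a two-sided 0.05 level for all tests. No power or sample size is given for Hypothesis 3. With independent tests, the asymptotic McNemar test holds that level: simulated error for 210 people with 4 tests each was 4.4 to 5.1% over an assumed discordance of 1 to 10%.

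**Maximum number of tests.** 2 + 2 = 4 kits per person; 210 × 4 = 840.

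**Formula.** Let D be +1, 0 or −1 for each test (disagreement favouring one reader, agreement, disagreement favouring the other). Let ρ be the within-person correlation of D and m the size-weighted number of tests per person, Σn²/Σn. Then

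- design effect DE = 1 + (m − 1)ρ
- true error = 2[1 − Φ(1.96/√DE)].

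The documents give no ρ, so 0.1, 0.3 and 0.5 are assumed.

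**Cluster size from planned uptake.** The sample size section assumes that about 60% of the intervention arm test within six months, on a Poisson model. I assume that the same uptake holds in both half-years and cap use at two kits per half-year.

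- Rate per half-year: −ln(0.40) = 0.916
- P(0) = 0.400; P(1) = 0.916 × 0.400 = 0.367; P(2, capped) = 0.233
- Mean per half-year = 0.367 + 2 × 0.233 = 0.833; per year 1.67
- Mean square per half-year = 0.367 + 4 × 0.233 = 1.300
- Halves independent: m = (2 × 1.300 + 2 × 0.833²)/1.667 = 2.4
- Same count in both halves: m = (4 × 1.300)/1.667 = 3.1

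**Full use of kits.** m = 4. If the 20% attrition means that 42 people receive only the first two kits, there are 168 × 4 + 42 × 2 = 756 tests and m = (168 × 16 + 42 × 4)/756 = 3.78.

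**True error of a nominal 5% asymptotic test**

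| m | ρ = 0 | ρ = 0.1 | ρ = 0.3 | ρ = 0.5 |
|---|---|---|---|---|
| 2.4 (planned uptake, halves independent) | 5% | 6.6% | 10.0% | 13.2% |
| 3.1 (planned uptake, same count in both halves) | 5% | 7.5% | 12.5% | 17.2% |
| 3.78 (full use, 20% attrition) | 5% | 8.3% | 14.8% | 20.5% |
| 4 (every kit used) | 5% | 8.6% | 15.5% | 21.5% |

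Example, m = 2.4 and ρ = 0.3: DE = 1 + 1.4 × 0.3 = 1.42; 1.96/√1.42 = 1.645; error 10%.

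**Simulation check** (210 people, 4 tests each, discordance 1 to 10%, 20,000 runs per setting):

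| Version | ρ = 0.1 | ρ = 0.3 | ρ = 0.5 |
|---|---|---|---|
| Asymptotic | 7.5–8.7% | 14.0–15.4% | 21.4–22.5% |
| Exact | 3.8–6.9% | 8.1–13.1% | 13.4–19.2% |

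A participant-clustered statistic, (sum of participant totals of D)² divided by the sum of their squares, gave 4.5 to 5.2% at 5 to 10% discordance. It was conservative at 1% (2.1 to 4.4%).

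**Sensitivity.** Participants must be non-reactive at baseline, and a positive read leads to referral for confirmation, so an infected participant will usually add about one truly positive test. With m near 1, DE is near 1. The Data Analysis section expects 25 to 40 positive tests. Split by allocation (an assumption), arm 1 would have 25 × 210/525 = 10 to 40 × 210/525 = 16.

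**The case against.** The strongest reply is that both the size and the certainty of the problem rest on a correlation that the documents do not give. That stands. At zero correlation nothing is wrong, and some design features would lower it: participants see the app's reading, and staff contact them when it differs from their own, so a misread can be corrected before the next quarterly test. Nothing shows that this removes the correlation. An exact McNemar test on very sparse disagreements at correlation 0.1 stays near or below 5%. But the plan does not specify the exact version, and at 0.3 that version still gives 8 to 13%.

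Four stronger readings are tempting and not supported:

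- **The sensitivity claim is inflated to the same degree.** It is not; the cluster size for truly positive tests is about one.
- **Error rates of 15 to 21% are to be expected.** They need all four kits used and a correlation of 0.3 to 0.5. The plan's own uptake implies fewer tests. Its 60% also refers to HIV testing in general, so app-read tests could be fewer still.
- **All uploads enter the comparison.** The text puts the methods on one set of tests, but sensitivity and specificity need a confirmatory result. Referral follows a positive read; after a negative read, the risk procedures refer only on request, although the Arm 1 text recommends confirmation for negatives too. The verified set is therefore smaller, and its cluster sizes are unknown. Repeated false positives from one person would still enter it.
- **The planned confidence intervals are too narrow.** None are planned for Hypothesis 3; those in the Data Analysis section are for testing rates.

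**Conclusion.** The point holds in limited form. As written, the Hypothesis 3 test ignores repeated tests from the same person. If disagreements are positively correlated within a participant, which is the reasonable expectation but not a documented fact, p-values are too small, mainly for specificity.

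Under the plan's uptake assumption, capped at two kits per half-year, the true error of a nominal 5% asymptotic test is about 7% at correlation 0.1, 10 to 12.5% at 0.3 and 13 to 17% at 0.5. The mechanism is certain; the size is not. This is a secondary goal with no stated power, so the primary comparison of testing rates is untouched. The analysis should still be corrected, because the omission is plain and the remedy cheap.

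**What to change.** In the mLab Image-Processing Data Analysis Plan, replace the plain McNemar test with a participant-clustered McNemar test, or with GEE using robust standard errors by participant, or with a bootstrap that resamples participants. Report each paired difference in sensitivity and specificity with a cluster-adjusted 95% confidence interval. Add a sensitivity analysis using one pre-specified test per participant.

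The cost is a few sentences of plan wording and no new data. P-values will be less favourable to part 2, and intervals wider than a naive analysis would give: at a design effect of 1.6, √1.6 = 1.26, about 26% wider. With very few disagreements the clustered test becomes conservative.

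This does not repair the separate problem that confirmatory results come mainly for tests read as positive. That needs its own solution.
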